Methods

1.1 Sample and Recruitment

The target population for this study is healthy athletes with a competitive background in cycling or other similar endurance-based sports, such as running, swimming, or cross-country skiing. The predicted sample representing this population will be individuals with a background in competitive endurance sports living and training in the Greater Vancouver area. Recruitment will take place by non-probability sampling methods, mainly by purposive sampling. Copies of a poster will be placed on public advertising boards around the University of British Columbia (UBC) Vancouver campus, as well as online on the UBC School of Kinesiology website, and will be distributed via email to local athletic clubs with athletes that may fit the inclusion and exclusion criteria to participate in the study (i.e., UBC Thunderbirds Cycling Sports Club, UBC Thunderbirds Triathlon Sports Club). This poster will be written in lay language, and designed to outline the inclusion and exclusion criteria for partaking in the study, the purpose and study design, potential risk and benefits to participating, and contact information for the primary investigator. The poster will also be circulated on social media (Facebook, Instagram, Strava, Reddit, etc.) to reach a greater audience of potential participants.

Inclusion Criteria		Exclusion Criteria	
1)	Currently training and/or competing in	1) History of smoking	
	endurance sport	2) Upper respiratory tract infection	
2)	Maximal oxygen consumption	within the last 4 weeks	
	(VO2max) greater than 60 ml/kg/min	3) Presence of any chronic respiratory	
	(males) or 55 ml/kg/min (females)	disease	
3)	Between the ages of 18 and 50	4) Current symptoms of, or current	
4)	Able to communicate sufficiently	infection with COVID-19	
	using the English language	5) Pregnant or suspect you may be	
5)	Taking hormonal birth control (female	pregnant	
	subjects only)		

Table 1. Inclusion and exclusion criteria for the proposed research study.

Table 1 above outlines the inclusion and exclusion criteria for the proposed research study. The first inclusion criterion, athletes currently training and/or competing in endurance sport, represents the target population for this study. As this study is designed in collaboration with the Canadian Sport Institute to access susceptibility to ozone exposure in national and international level athletes, it is logical to only recruit athletes to maximize transferability of results. Similarly, the second inclusion criterion, maximal oxygen consumption (VO2max) greater than 60 ml/kg/min (males) or 55 ml/kg/min (females), helps ensure that the sample is representative of the target population. Although elite endurance athletes have been shown to achieve VO2max values well above 70 ml/kg/min (Jones et al., 2021), such athletes are unlikely to participate in the proposed study to avoid interrupting their rigid training programs. The specified VO2max requirement will allow for well-trained individuals in roughly the ~90th percentile of aerobic fitness (Kaminsky et al., 2022), without the time and training constraints of professional athletes to participate in the proposed study. Additionally, by reducing the variability of fitness level between participants, it is likely that the variability between minute ventilation during exercise will also be reduced, helping ensure that a similar effective dose of pollution is delivered to all participants. The third inclusion criterion, between the ages of 18 and 50, reduces the likelihood of potential harm to participants from ozone exposure and exercise. The human respiratory tract is particularly vulnerable to air pollution exposure during periods of development, which may lead to short- and long-term health effects (Goldizen et al., 2016). As the respiratory tract is not fully developed until roughly 18-20 years old (Goldizen et al., 2016), only subjects over the age of 18 will be permitted to participate. Similarly, based on the increased risk of cardiovascular and respiratory diseases (Manisalidis et al., 2020), as well as cognitive impairment (Gao et al., 2022), adults over the age of 50 will not be permitted to

Page 2 of 23

participate due to increased risk. The fourth inclusion criterion, ability to communicate sufficiently in the English language, ensures that subjects are able to fully understand study procedures, have the ability to ask questions, and provide informed consent.

The fifth inclusion criteria, taking hormonal birth control (females only), minimizes potential confounding factors on inflammatory responses in females due to the potential protective effects of estrogen (Birukova et al., 2019). By removing variation in sex hormones that naturally occurs throughout the menstrual cycle between experimental visits, greater confidence can be had in the results.

The first and second exclusion criteria, history of smoking and presence of upper respiratory tract infection in the last 4 weeks, avoids potential biasing of expired nitric oxide (FeNO) measurements. It is well recognized that both acute and chronic exposure to smoking is associated with significant reductions in FeNO, due to increased breakdown of nitric oxide (NO) (Malinovschi et al., 2006). Additionally, acute rhinovirus infections are shown to increase FeNO 50-150% due to upregulated inducible nitric oxide synthase (iNOS) in the respiratory tract (Bjermer et al., 2014). As such, exclusion of smokers and those not fully recovered from infection will best ensure FeNO measurements are indicative of lung inflammation. The third exclusion criteria, presence of any chronic respiratory disease, helps mitigate the influence of such diseases on spirometry measures. Those with respiratory diseases that cause airway hyperreactivity, such as asthma, have been shown to experience greater decreases in pulmonary function in response to ozone than healthy individuals (Kleeberger, 1995). As this study aims to establish susceptibility and ventilatory responses to ozone in healthy subjects, removal of subjects with chronic respiratory diseases will limit potentially conflicting factors. The fourth exclusion criteria, current symptoms or infection with COVID-19, helps mitigate any potential influences of both short- and long-COVID-19 symptoms, as well as protecting members of the research team. Symptoms commonly attributed to COVID-19 include difficulty breathing, coughing, and general weakness (Çalıca Utku et al., 2020) that may impact ability to properly perform exercise or spirometry measures.

The fifth exclusion criteria, pregnant or suspect you may be pregnant, minimizes risk to participants. As O3 exposure is shown to lead to negative health outcomes in pregnant women, such as increasing likelihood of preterm birth (Rappazzo et al., 2021), avoiding testing of subjects who may be pregnant increases participant safety.

Sample size was calculated using data from previous studies that examined changes in FEV1 in athletes following ozone exposure during exercise. A similar crossover design in elite athletes utilizing ozone exposure at 200ppb found a 0.95-litre reduction in FEV1 following exercise, with a standard deviation of post-exercise measures of 0.86-litres (Gong et al., 1986). Calculation for a crossover design based on analysis of variance F-tests using these values with a power of 0.8 and an alpha level of 0.05 led to a sample size of 15 subjects. Sample size will be increased to 24 to include female subjects.

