1.4 Procedures

Participants will visit the laboratory for testing on 4 occasions. A minimum of 72-hours washout is required between visits. Before each session involving exercise (Visits 1,3,4), subjects will be asked to prepare as if each visit was a competition or important training session in their training schedule, and to ensure preparation is as similar as possible prior to each visit to minimize variability in results. This will include, but is not limited to, avoiding alcohol and strenuous exercise for 24 hours, ensuring a proper sleep the night prior, and consuming a pre-exercise meal that they are accustomed to timed appropriately prior to each visit. However, participants will be advised not to consume any ergogenic aids (i.e., sodium bicarbonate) or stimulants (i.e., significant doses of caffeine) for 24 hours prior to each visit, even if they typically utilize such strategies during competition. All visits involving exercise (Visits 1,3,4) will be performed at a similar time of day in order to avoid any diurnal variation in exercise performance (Kusumoto et al., 2021).

The first visit will involve participant consent, screening for inclusion based on a maximal exercise test, and familiarization with pulmonary function measurements. Participants will first re-read the consent form. They will be given the opportunity to ask any questions related to their involvement, then be asked to sign the informed consent. Participants will also complete a PAR-Q+ form, which will be reviewed prior to partaking any exercise in the laboratory. Participants will then be familiarized with pulmonary function testing equipment and protocols, and undergo resting spirometry and FeNO measurements (described in detail above).

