The second visit will consist of resting exposure to ozone and pulmonary function tests. Subjects will conduct pre-ozone resting spirometry, FeNO, dyspnea, and symptom measurements, followed by 2-hours of resting O₃ exposure at 750ppb. During the resting exposure, subjects will be seated with a three-way non-rebreathe valve and mouthpiece connected via tube to the ozone chamber. Nose-clips will be worn for the entirety of the protocol, and expired volumes will be analyzed to determine average minute ventilation, and effective dose of O3 (minute ventilation x O₃ concentration x exposure duration) (Silverman et al., 1976). Subjects will be permitted to use personal electronic devices (phone, laptop, tablet etc.) during exposure, provided no significant movement is required. Following exposure, subjects will complete identical spirometry, FeNO, symptoms, and dyspnea measurements immediately and 30-minutes post-exposure to that completed pre-exposure. Post-exposure and pre-exposure values will be compared to determine resting response to O3.

The third and fourth visits will consist of identical procedures, randomized as to the order of the O3 and control conditions. During both experimental trials, a lab member other than the researcher will control the O₃ concentration in order to maintain blinding of the participant and the researcher as to the condition. During the O₃ exposure, subjects will receive 170ppb O₃, and during the control exposure subjects will receive room air (typically <10ppb O₃). Upon arrival in the laboratory, the researcher will confirm that pre-visit requirements (detailed above) are met, prior to resting spirometry, FeNO, symptoms, and dyspnea measurements. Subjects will then be connected via tube and mouthpiece/valve to the O₃ chamber. While remaining connected to the O₃ chamber, participants will then complete a standardized warmup on the Velotron of 25-

Page 10 of 23

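### Requiring hormonal birth control does not by itself remove hormone variation between visits: for women on cyclic methods, the resting, ozone and air visits can fall in different hormone phases, which mainly adds noise

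*Combined protocol and SAP*

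**What the plan says.** Table 1 in section 1.1 lists "Taking hormonal birth control (female" subjects only) as the fifth inclusion criterion, with no method or regimen named. The accompanying text explains that "taking hormonal birth control (females only), minimizes potential confounding factors on inflammatory responses in females due to the potential protective effects of estrogen", and then states how this is achieved: "By removing variation in sex hormones that naturally occurs throughout the menstrual cycle between experimental visits", which the plan takes as grounds for more trust in its findings.

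Visit timing is set in sections 1.3 and 1.4. The spacing rule is a minimum only: "A minimum of 72-hours washout is required between visits". Visits that involve exercise (1, 3 and 4) "will be performed at a similar time of day in order to avoid any diurnal variation in exercise performance". For the two conditions, "The third and fourth visits will consist of identical procedures, randomized as to the order of the O3 and control conditions".

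The pre-visit preparation list in section 1.4 is open-ended. It covers alcohol, exercise, sleep, food, ergogenic aids and stimulants, and does not mention contraceptive phase. Section 1.5 names no phase covariate. No section sets a maximum gap between visits or asks for method or pack day to be recorded.

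**The concern.** The criterion is meant to hold hormones steady within a woman from one visit to the next. Being on a hormonal method does that only if the method gives constant exposure, or if the visits fall in the same part of its cycle. The plan requires neither. Followed exactly, it lets Visit 3 fall on active-hormone days and Visit 4 on hormone-free days, or puts the Visit 2 resting test in one phase and the ozone exercise trial in the other.

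The plan itself names estrogen as a possible confounder of inflammatory responses, and it gives up recruiting women who do not use hormonal contraception for that reason. It therefore bears the recruitment cost without securing the property it relies on. The measure most exposed is FeNO, which section 1.2 uses as the marker of lung inflammation and section 1.5 compares between the two trials.

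**Working it through.** **The plan's own figure.** The only related number is the sample size. A paired t-test with difference 0.95 L, SD of the difference 0.86 × √2 L (zero within-subject correlation), two-sided alpha 0.05 and n = 15 has power 0.803, so the plan's 15 reproduces. This point does not affect it. The final figure of 24 matters only because 24 − 15 = 9 is one possible reading of how many women will enrol; the plan gives no split by sex.

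**Inputs.** From the documents: minimum gap of 3 days, no maximum, no link to contraceptive day. Assumed, because the documents describe no regimen: a 28-day cycle with 21 active and 7 hormone-free days, or 24 and 4; Visit 3 on a uniformly random cycle day. Continuous methods have no hormone-free days.

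**Ozone and air visits in different phases.** With h hormone-free days and a gap of g days, for gaps from 3 up to 21 days, P(different) = 2 × min(g, h) / 28.

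| Gap | 21/7 | 24/4 | Continuous |
|---|---|---|---|
| 3 days | 6/28 = 0.21 | 6/28 = 0.21 | 0 |
| 4 days | 8/28 = 0.29 | 8/28 = 0.29 | 0 |
| 5 days | 10/28 = 0.36 | 8/28 = 0.29 | 0 |
| 7 to 21 days | 14/28 = 0.50 | 8/28 = 0.29 | 0 |

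At a gap of exactly 28 days the probability is 0. If the two dates are unrelated it is 2 × 0.75 × 0.25 = 0.375 for 21/7 and 2 × 24 × 4 / 28² = 0.245 for 24/4.

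**Visits 2, 3 and 4 together, 21/7.**
- At 7-day spacing, all three visits are active for 7 of 28 start days and never all hormone-free, so phases are mixed for 21/28 = 0.75.
- At 3-day spacing, 15 start days give three active visits and 1 gives three hormone-free visits, so phases are mixed for 12/28 = 0.43.

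**Number of women affected.** If there were nine women and all used 21/7, the expected number with mismatched ozone and air visits would be 9 × 0.214 = 1.9 to 9 × 0.50 = 4.5. With all on 24/4 it would be 1.9 to 9 × 0.286 = 2.6. With all on continuous methods it would be 0.

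**Effect on the overall ozone estimate.** Let a phase change shift a woman's ozone-minus-air difference by d, with its sign random because order is randomized. The SD of the resulting disturbance to a 24-subject mean difference is √(expected mismatched pairs) × d / 24. With nine women on 21/7 this is √1.93 / 24 = 0.06d to √4.5 / 24 = 0.09d. The documents give no value for d.

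**The case against.** The strongest reply has five parts.

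- **Randomized order.** A reader might infer that a phase change between Visits 3 and 4 biases the ozone comparison. The documents do not support that. Within one woman the phase change cannot be separated from the condition, but across women it is as likely to favour ozone as air. What remains is noise and chance imbalance. The 0.06d to 0.09d above is small unless d is large, and section 1.5 plans no female-only analysis. This part stands.
- **Pre-exposure measures.** Spirometry and FeNO are taken before exposure at Visits 2, 3 and 4, so a shift in resting level cancels wherever change is analysed. The rest-exercise regression uses reductions, so only a phase effect on the ozone response itself would disturb it. This stands for the regression. It is less secure for FeNO, because section 1.5 does not say whether the mixed model uses change or level.
- **Scope.** Section 1.1 ties estrogen to inflammatory responses only. Nothing in the documents links contraceptive phase to FEV1 or the other spirometry measures, so the concern should centre on FeNO. This stands.
- **Headcount.** A reader might also infer that two to five of nine women will be mismatched. That requires all nine added participants to be women and all of them to use 21/7. Neither is stated, and the range starts at 0.
- **Wording.** The sentence in section 1.1 concerns natural menstrual-cycle variation, and the text also speaks of minimizing confounding. Contraception may well reduce that variation. This is fair, but the sentence goes on to rely on removal between visits, which the timing rules do not secure.

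**Conclusion.** The point holds in a limited form. The plan as written does not secure stable hormone exposure between visits for women on cyclic methods. The consequence is added within-woman noise and possible chance imbalance, chiefly for FeNO. The mismatch probabilities, from 0 for continuous methods up to 50% for 21/7, rest on assumed regimens and random start days. They count calendar mismatches and say nothing about the size of any effect on an estimate. That size is unknown, as are the number of women and their mix of methods. The sample size calculation is untouched. The change is still worth making before enrolment: it is cheap, it concerns a confounder the plan itself names, and pack day is hard to recover reliably afterwards.

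**What to change.** 1. Record contraceptive method and pack day (or its equivalent) at every visit.
2. For participants on a cyclic method, book Visits 2, 3 and 4 within active-hormone days, and re-book where possible if a visit would fall outside them. Three visits with two 72-hour gaps need at least 2 × 3 = 6 days, which fits within 21 active days. Participants on continuous methods need no change.
3. Keep every participant in the main analysis. Add a sensitivity analysis of FeNO that leaves out pairs whose ozone and air visits fell in different phases.
4. In section 1.1, change *removing* to *reducing*.

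The cost is two questions per visit, one booking rule and one sensitivity analysis. The downside is slightly less scheduling freedom for participants on cyclic methods.

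### No re-check of the plan's own infection exclusion is written for Visits 2–4, so a recent infection before only one of Visits 3 and 4 can add noise to the ozone–air FeNO comparison

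*Combined protocol and SAP*

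**What the plan says.** Section 1.1 states what the infection criterion is for. Together with the smoking exclusion, "presence of upper respiratory tract infection in the last 4 weeks, avoids potential biasing of expired nitric oxide (FeNO) measurements". The reason given is that "acute rhinovirus infections are shown to increase FeNO 50-150" per cent, and the section concludes that "exclusion of smokers and those not fully recovered from infection will best ensure FeNO measurements are indicative of lung inflammation". Exclusion criterion 4 covers current COVID-19 symptoms or infection, and is justified partly by the safety of the research team. Table 1 gives no timing for checking either criterion.

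Section 1.4 places screening at the first attendance: "The first visit will involve participant consent, screening for inclusion based on a maximal exercise test". On spacing it says "A minimum of 72-hours washout is required between visits"; no maximum is given. The preparation instructions are open-ended: "This will include, but is not limited to, avoiding alcohol and strenuous exercise for 24 hours, ensuring a proper sleep the night prior". The list continues with the pre-exercise meal, ergogenic aids and stimulants. For Visits 3 and 4 the plan adds that "Upon arrival in the laboratory, the researcher will confirm that pre-visit requirements (detailed above) are met, prior to resting spirometry, FeNO, symptoms, and dyspnea measurements". No arrival check is written for Visit 2.

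Section 1.5 compares FeNO between the two experimental trials by mixed models, listed as further analysis. It does not say whether the pre-exposure value enters the model.

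**The concern.** The reason for the 4-week rule applies on every day FeNO is measured, and FeNO is measured at Visits 2, 3 and 4 as well as Visit 1. The same section requires hormonal contraception to remove variation between experimental visits, so the plan already treats within-person stability as important. It writes no matching protection against an infection that starts after entry.

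Someone visibly ill would probably be postponed in practice. The harder case is a subject who had a cold one to three weeks before Visit 3 or Visit 4 and now feels well. The 4-week window exists for that subject, and nothing written would stop the visit. In a 24-person crossover, such a subject contributes a paired FeNO difference that reflects infection as well as ozone. A current cold would also affect the nose, throat and chest symptom ratings. Without a written rule, affected visits would be handled case by case, possibly after the data have been seen.

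**Working it through.** **1. Is a re-check written?**

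| Visit | FeNO measured | Arrival check written | Infection named |
|---|---|---|---|
| 1 | yes | screening for inclusion | in Table 1, without timing |
| 2 | yes | none | no |
| 3 and 4 | yes | preparation requirements | no |

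The open-ended wording extends a list of preparation behaviours. Health status is not among them.

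**2. The plan's own figures.** The plan gives no FeNO sample size or precision. Its figure of 15 is for FEV1. It reproduces with a paired t-test, difference 0.95 L, SD of the difference 0.86 × √2 = 1.216 L, two-sided alpha 0.05: n = 15, power 0.803. It does not bear on this point. The inputs used below are N = 24 and s = 0.50 to 1.50 (section 1.1, acute infection).

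**3. Shift in the mean ozone–air difference.** With k subjects infected before the same condition's visit, each with FeNO otherwise near the group mean, and a raw post-versus-post contrast, shift = k × s / N.

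- k = 1: 0.50/24 = 2.1%; 1.00/24 = 4.2%; 1.50/24 = 6.3% of mean FeNO.
- k = 2, both before the same condition: 4.2% to 12.5%.

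**4. Direction.** Order is randomised, so an infection unrelated to condition is equally likely to precede ozone or air. The expected shift is zero. With one infected subject, the added random error in the mean difference has SD s/24, again 2.1% to 6.3%.

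**5. Precision.** The documents give no SD for paired FeNO differences, so these are assumed values.

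- Raw scale: variance factor = [SD² + (1/24)(23/24)s²] / SD².
- Log scale: variance factor = [SD² + (ln(1+s))²/24] / SD².

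| Scale, assumed SD | s = 0.5 | s = 1.0 | s = 1.5 |
|---|---|---|---|
| Raw, 20% of mean | 1.25 | 2.00 | 3.25 |
| Raw, 30% of mean | 1.11 | 1.44 | 2.00 |
| Log, 0.10 | 1.69 | 3.00 | 4.50 |
| Log, 0.20 | 1.17 | 1.50 | 1.87 |
| Log, 0.30 | 1.08 | 1.22 | 1.39 |

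At log SD 0.20, the difference detectable with 80% power rises from 12.7% to 13.8% (s = 0.5) or 17.8% (s = 1.5).

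**6. What the same-visit baseline would remove.** If infection adds a constant a to both readings, (post + a) − (pre + a) = post − pre. If it multiplies both by (1 + s), the ratio post/pre is unchanged. An elevation that is stable within the visit therefore cancels on the matching scale. Used as a covariate, the baseline removes it in part, depending on the fitted slope.

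**7. How likely is it?** The documents give no infection rate. If the per-person risk over the experimental visits is p, the chance of at least one case is 1 − (1 − p)^24: 21% at p = 1%, 38% at 2%, 71% at 5%, 92% at 10%.

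**The case against.** A reader might infer that the criterion was meant to lapse after entry. The documents do not say so. Table 1 sets no timing, the preparation list is expressly not exhaustive, and a COVID-19 criterion aimed partly at protecting staff makes most sense at every attendance. What stands is narrower: no re-check is written.

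A reader might also infer that the ozone–air comparison could move by 50–150%, or that it would be biased. Neither is supported. The figure is per infected person and for acute infection, and randomised order leaves noise and chance imbalance. Nor do the documents support saying that one case costs half the sample. That needs a raw-scale SD of 20% and a 100% rise; with an SD of 30% the variance factor is 1.44.

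The strongest objection is that the acute figure is being applied to people who have recovered. Acutely ill subjects are the ones most likely to be postponed, and the documents give no value for residual elevation weeks later. This stands, and it makes the 2–6% an upper bound.

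The design also has partial safeguards. Resting FeNO and symptom ratings for nose, throat, chest and general health are recorded before exposure at both experimental visits. They could reveal a current infection, and the FeNO baseline could absorb a stable elevation. However, no action threshold is set, section 1.5 does not commit to using the baseline, and symptom ratings may miss a recent infection that no longer causes symptoms.

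Finally, FeNO is listed under further analysis and the sample size rests on FEV1, which limits the importance. Visit 2 FeNO does not enter the ozone–air comparison at all.

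**Conclusion.** The gap is real and modest. The plan states an infection criterion to protect FeNO but writes no re-check of it, or of current COVID-19 symptoms, for Visits 2–4. It also has no upper limit on visit spacing and no rule for an affected visit. Followed as written, it would test a subject who had a cold one to three weeks earlier.

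The consequence is lost precision and chance imbalance in the FeNO comparison. The upper bound is a shift of about 2–6% of mean FeNO per affected subject of 24. It rests on the acute 50–150% figure, an affected subject with FeNO near the group mean, infection before only one of Visits 3 and 4, and no baseline adjustment. The variance factors rest on assumed SDs and serve only as illustration. The case for acting is that the change is cheap and uses the plan's own criterion. The trial's main comparisons are not shown to be at risk.

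**What to change.** - In sections 1.1 and 1.4, state that exclusion criteria 2 and 4 are asked again on arrival at Visits 2, 3 and 4, and that the visit is rebooked until they are met. Ask and record the answer before exposure, with subject and researcher still blinded, so that rebooking cannot depend on condition.
- Where rebooking is impossible, flag the visit and repeat the FeNO analysis without it, as a pre-specified sensitivity analysis.
- In section 1.5, include the same-visit pre-exposure FeNO in the FeNO mixed model and name the scale. The measurement is already collected.

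The cost is one question per arrival. The downside is that some visits will be postponed by up to about 4 weeks. This lengthens the interval from the Visit 1 test that sets the workloads, with some risk of fitness drift in athletes who are still training. The dates of all visits should be recorded so that this interval can be reported.
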